5.2.3 Description for Use of Pre-vs-Post Subjective Patient Questionnaire (PROWL)³⁴⁻³⁷

The pre-operative and post-operative PROWL (Patient Reported Outcomes with LASIK) questionnaires were developed and validated to sample patient impressions of LASIK surgery adequacy for improved vision and activities such as night driving, sports, etc. dependent on good patient vision. Select PROWL questions and domains will be analyzed for this study, not the PROWL-PRQ and PROWL-POQ questionnaires in their entirety. However, the entire PROWL questionnaires are included in this study since they were validated as such.^{36,37} PROWL questions and domains relating to subject subjective preoperative and postoperative impressions of their LASIK surgery^{36,37} (including clusters of questions or domains for vision clarity, far vision, near vision, patient satisfaction with vision and with surgery, and quality of life) and patient-perceived safety assessments (i.e., driving, dry eye [OSDI domains 1 and 3],^{38,39} and the frequency, severity, and bothersomeness of visual symptoms) will be analyzed as described in Section 8.5 and Section 9.6.3.3.1 and by the methods and respective scoring methodologies for each of the above domains as detailed in the study Statistical Analysis Plan. The PROWL questionnaires^{34, 35} should be completed by the study subject in a secluded area, free of directions from clinical staff.

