8.5 Symptoms

Subjects will complete subject PROWL questionnaires at the preoperative visit and each scheduled study visit from the 3-month postoperative visit on. The PROWL questionnaires should be completed by the study subject in a secluded area, free of directions from clinical staff. Subjects will be asked to complete all PROWL questions to the best of their ability, and only certain PROWL domains will be analyzed for the purposes of this protocol. For domains dealing with symptoms and specifically evaluated with the PROWL questionnaire for this study, patients will grade the frequency, severity and inconvenience (bothersomeness) of their glare, halos, double images, and starburst visual symptoms as part of the PROWL symptom domain (questions 45-64 in the PROWL-PRQ³⁴ questionnaire and questions 42-61 in the PROWL-POQ³⁵ questionnaire). Results from domain 1 (visual function) and domain 3 (environmental stimuli) of the Ocular Surface Disease Index (OSDI) questionnaire ⁴¹ (questions 65-72 of the PROWL-PRQ³⁴ questionnaire and question 62-69 of the PROWL-POQ³⁵ questionnaire) also will be

TENEO 317 1.28 US

evaluated pre- and post-surgery for evidence of dry eye association with LASIK surgery, as will questions related to far vision (PROWL-PRQ questions 16-18 and 28-29, and PROWL-POQ questions 10-12 and 22-23), near vision (PROWL-PRQ questions 24-27 and PROWL-POQ questions 18-21), and driving (PROWL-PRQ questions 12-18 and PROWL-POQ questions 6-12). For more detail, see Section 9.6.3.3.1 and methods of symptom data analysis in the Statistical Analysis Plan.

Subjective results will be presented as percentages ("better" or "worse") and appropriate statistical analyses for change from baseline will be conducted as described in the study Statistical Analysis Plan, but the data will not be included in the analysis of "Incidence of Adverse Events". The subjective subject questionnaires used are:

- Pre-operative PROWL-PRQ ³⁴
- Post-operative PROWL-POQ ³⁵

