6.5.8.7 Schirmer's Test

Appropriate commercial paper strips for conducting a Schirmer's test without anesthesia are placed in the inferior fornix extending outward of both eyes and subjects are instructed to close their eyes for 5 minutes. The test strips are then removed, and the migration distance of strip wetness is measured in mm. No topical anesthetic may be used.

Schirmer's test is conducted in each eye at the Preoperative Visit and postoperatively at the Month 6 Visit. Tear fluid secretion from the Schirmer's test will not be summarized in a table.

A data listing by subject of Schirmer's test results will be provided.

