6.5.8.9 PROWL Questionnaire

The PROWL-PRQ and PROWL-POQ will be administered to all subjects. Subjects will complete PROWL questionnaires at the Preoperative Visit and postoperatively at the Month 3, Month 6, and Month 9 Visits.

Results obtained both pre- and post-LASIK surgery will be assessed for selected topic domains of near vision, far vision, eye dryness, subject symptoms, driving, and vision clarity. **Table 3** describes the specific pre-operative PROWL-PRQ and post-operative PROWL-POQ questions to be analyzed for each of these topic domains. Normalization of individual or domain scores, if required, will be done as described in the Hays RD paper [5] or relevant primary references annotated in the PROWL questionnaire reference. Domain score for each subject will be provided as the average score of all questions within a domain after normalization as shown in **Table 3a**.

Normalized results for other PROWL-PRQ and/or PROWL-POQ categories of vision satisfaction, vision clarity, and satisfaction with LASIK surgery will be analyzed. **Table 4** describes the specific PROWL-PRQ and PROWL-POQ questions to be summarized for each of these categories with normalization score details provided in **Table 4a**.

Domains presented in Tables 3 and 4 will be summarized by study visit using continuous descriptive statistics including change from baseline.

Topics - Pre and Post LASIK surgery	PROWL-PRQ questions	PROWL-POQ questions
Far Vision	16-18 and 28-29	10-12 and 22-23
Near Vision	19 and 24-27	13 and 18-21
Eye Dryness	65-72	62-69
Subject Symptoms	45-64	42-61
Driving	12-18	6-12
Vision Clarity	34-36a	28-30a

Table 3. PROWL Topic Domain Categories and Domain Questions to be Analyzed

Table 4a	. Normalized	Scores for	PROWL	Questions	in Table 3
----------	--------------	------------	-------	-----------	-------------------

Topics - Pre and Post LASIK surgery	PROWL-PRQ questions	PROWL-POQ questions	Normalized Score
Far Vision	16-17	10-11	No difficulty at all =100 A little difficulty = 75 Moderate difficulty = 50 A lot of difficulty = 25 Never drive at night because of vision, or Never drive in these condition because of vision = 0 Never drive at night for other reasons or Never drive in these condition for other reasons = N/A
		•	No difficulty at all =100 A little difficulty = 200/3 Moderate difficulty = 100/3 A lot of difficulty = 0 all questions within the domain)/(total

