number of questions answered) Note: Questions with answers as N/A will be treated as not answer excluded from the mean domain score calculation.			ore calculation.
Near Vision	19	13	No difficulty at all =100

			A little difficulty = $200/3$
			Moderate difficulty = $100/3$
			A lot of difficulty = 0
			No difficulty at all =100
			A little difficulty $= 75$
			Moderate difficulty $= 50$
			A lot of difficulty = 25
		10.00	Never try to do these activities
	24-26	18-20	because of vision or Never try to do
			this because of vision $= 0$
			Never do these activities for other
			reasons or Never do this for other
			reason = N/A
			Yes, many = 0
	27	21	
	21	21	Yes, one or a few $= 50$
	D i		No = 100
			all questions within the domain)/(total
	number of question	,	
	-		A will be treated as not answered and
	excluded from the	e calculation.	
			None of the time $= 4$
	65-72		Some of the time $= 3$
		62-69	Half of the time $= 2$
Eye Dryness			Most of the Time $= 1$
			All of the Time $= 0$
	Domain score =	[(sum of scores of	of all questions within the domain) x
	100]/[(total number of questions answered) x 4].		
		1	Scoring should always value best
			health as $= 100$, and other optional
			choices to range down to $= 0$.
			Scoring steps then should recognize
			the number of steps from 0 to 100
	45-64	42-61	units.
Subject Symptoms	HJ-04	42-01	units.
(including 4	Double Images:	Double Images:	Example 1) PRQ61a: In the last 7
symptom groups,	45-49	42-46	1 / ~
double images, glare, halo, and starbursts)	Glare: 50-54	42-40 Glare: 47-51	days, how often have you seen starbursts when you are wearing
	Halo: 55-59	Halo: 52-56	your best vision correction (glasses
, ,	Starburst: 60-64	Starburst: 57-61	or contact lenses)?
			I do not wear glasses or contact
			lenses = N/A
			Never $= 100$
	1	1	Rarely $= 75$
			Sometimes = 50

			Often = 25
			Always = 0
	Domain scor	e = (sum of score	Example 2). PRQ60: In the last 7 days, have you seen any starbursts? Yes, but ONLY when NOT wearing glasses or contact lenses = 100/3 Yes, but ONLY when wearing glasses or contact lenses = 200/3 Yes, when wearing AND when not wearing glasses or contact lenses = 0 No, not at all = 100 es of all questions within the domain)/(total
			-
		estions answered	e for each symptom group. Questions with
			ed as not answered and excluded from the
	calculation.	wa wili be treat	ed as not answered and excluded from the
		67	Ves en no secrito a norde d
	12-13	6-7	Yes or no, no scoring needed

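### The SAP's single Eye Dryness score averages a visual-function domain with an environmental domain, so worsening on the environmental items can be diluted and, under some conditions, offset

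*SAP*

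**What the plan says.** Protocol 8.5 says that the dry-eye block consists of "Results from domain 1 (visual function) and domain 3 (environmental stimuli) of the Ocular Surface Disease Index (OSDI) questionnaire", at "questions 65-72 of the PROWL-PRQ" and the matching post-operative questions 62-69. It is to be examined before and after surgery "for evidence of dry eye association with LASIK surgery". Protocol 5.2.3 places it among the patient-perceived safety assessments, defined through both OSDI domains, and leaves the scoring to the SAP. Protocol Table 3 lists the eight questions as one eye-dryness topic.

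SAP 6.5.8.9 keeps that single topic. Its general rule is "Domain score for each subject will be provided as the average score of all questions within a domain after normalization as shown in" Table 3a (captioned 4a in the body of the SAP). The operative text is the Eye Dryness row of that table. Each answer is scored from 4 (best) to 0 (worst), and the score is the sum times 100, divided by four times the number of questions answered. The result is summarised by visit with continuous statistics and change from baseline. No separate score is planned for OSDI domain 1 or domain 3.

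Other dryness information in the SAP:

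- Dry eye is a listed complication, tabulated by visit and overall (6.5.8.4).
- PROWL answers are listed by subject and visit (6.5.8.9).
- Schirmer's results are listed, but "Tear fluid secretion from the Schirmer's test will not be summarized in a table" (6.5.8.7). Protocol 9.6.3.3 had named them among the safety summaries, and SAP 6.6 declares the change.

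**The concern.** The device is meant to improve vision, and dry eye is one of the LASIK risks named in Protocol 3.3. Half of what this safety score is built from is a domain that the protocol itself calls visual function. If the treatment benefit raises those items while dryness lowers the environmental items, the mean of the two cannot show which happened. A flat or slightly positive Eye Dryness change could then be read as reassurance when one of its two components has worsened.

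What is at stake is the reading of one descriptive patient-reported safety result, the only dryness measure that the SAP tabulates on a scale.

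**Working it through.** **Inputs**

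- Number of items: 72 - 65 + 1 = 8 before surgery and 69 - 62 + 1 = 8 after (Protocol 8.5).
- Score: sum × 100 / (answered × 4), from the Eye Dryness row of the SAP table. With 8 answers it runs from 0 to 100, and 100 is best. One answer category is worth 100/4 = 25 points on an item.
- Item split between the two domains: not in the documents. Assumed k = 3, 4 or 5 visual items, with 8 - k environmental.
- Changes in each domain: not in the documents. The values below are illustrations.

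The plan states no expected dryness change, so there is no figure to reproduce.

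**Formula**

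With all items answered, and d1 and d3 the changes in the visual and environmental scores:

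pooled change = [k·d1 + (8 - k)·d3] / 8

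Subtracting d3 gives pooled change - d3 = k(d1 - d3)/8. So whatever the split, an environmental worsening is understated whenever the visual domain falls by less than the environmental one. If both fall equally, nothing is lost.

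**Results**

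| d1 | d3 | k = 3 | k = 4 | k = 5 |
|---|---|---|---|---|
| 0 | -10 | -50/8 = -6.3 | -40/8 = -5.0 | -30/8 = -3.8 |
| +10 | -10 | (30 - 50)/8 = -2.5 | (40 - 40)/8 = 0.0 | (50 - 30)/8 = +2.5 |
| +10 | -15 | (30 - 75)/8 = -5.6 | (40 - 60)/8 = -2.5 | (50 - 45)/8 = +0.6 |
| 0 | -25 | -125/8 = -15.6 | -100/8 = -12.5 | -75/8 = -9.4 |

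The last row is a one-category worsening on every environmental item with no visual change.

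**When is cancellation complete?**

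It needs d1 = -d3·(8 - k)/k, and the visual score must have room to rise by that amount. For d3 = -25:

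- k = 3: gain of 25 × 5/3 = 41.7, so visual baseline at most 58.3
- k = 4: gain of 25 × 4/4 = 25.0, so visual baseline at most 75.0
- k = 5: gain of 25 × 3/5 = 15.0, so visual baseline at most 85.0

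A concrete case with k = 5: all eight items start at 3, a score of 75. After surgery three visual items rise to 4 and all three environmental items fall to 2. The visual score changes by +15 and the environmental score by -25. The pooled score is still 75, a change of 0.

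If instead every item starts at 4, the visual items cannot rise. With k = 5, the same environmental fall moves the pooled score from 100 to 90.6. The worsening is diluted but visible.

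**The case against.** The strongest reply is that a visual gain on these items is not established. The documents do not give their wording or say whether they are answered with the subject's usual correction. Inclusion requires corrected acuity of 20/25 or better, and at least one other PROWL item asks about vision with best correction. If these items describe corrected daily vision, removing the refractive error need not raise them. Dryness could also lower domain 1, and then little or nothing is masked. This stands: the size and even the direction of the visual change are unknown, so the table above is illustration only.

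A second reply is that pooling is not an SAP invention. Protocol Table 3 already groups the eight questions, and the SAP refers to published scoring papers that are not available here. This also stands. The point is about what a pooled score alone can show. It is not a finding that the scoring departs from its source.

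Two stronger readings are tempting, and the documents support neither.

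- *A dryness signal would vanish from the report.* It would not. Dry eye is tabulated as a complication, and questionnaire answers and Schirmer's results are listed. Those sources do not replace a tabulated scale, however: the complication entry has no stated criterion in Protocol 8.4 or SAP 6.5.8.4, and listings are not summaries.
- *Domain 1 is contamination and dryness should be read from domain 3 alone.* The protocol counts both domains as dry-eye evidence in 5.2.3 and 8.5, and nothing in either document supports dropping one.

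**Conclusion.** The concern holds in limited form. The Eye Dryness score combines two domains that the protocol names separately, in a trial whose treatment may move one of them for reasons other than dryness, and no domain score is planned. An environmental worsening is diluted at any split unless the visual domain falls at least as far. Complete offset needs a visual gain large enough for the split and a baseline low enough to allow it.

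Under the assumed split of 3 to 5 visual items, an environmental change of -10 would be reported as -6.3 to -3.8 with no visual change, and as -2.5 to +2.5 with a visual gain of 10. These figures rest on the assumed split, the assumed changes and complete answers.

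The score is descriptive, with no test or threshold attached. The primary endpoints, power and success criterion are untouched. This is a low-cost improvement to safety reporting.

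**What to change.** In SAP 6.5.8.9, in the topic table and its scoring table (Tables 3 and 3a in the SAP's list of tables):

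1. Keep the pooled Eye Dryness score.
2. Add a score for OSDI domain 1 (visual function) and one for OSDI domain 3 (environmental stimuli), using the same 0-100 formula, and state which questions belong to each.
3. Summarise all three by visit with change from baseline.
4. State that the dry-eye result is read from the three rows together.

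This follows the SAP's own handling of Subject Symptoms, which it divides into four symptom groups with their own question ranges. All the data are already collected. The cost is a few lines of SAP text and two more rows per visit.

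### The PROWL symptom gate item scores when glasses are worn as well as whether the symptom is present, so its change from baseline mixes the two; the protocol's better/worse percentages are also dropped without being declared.

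*SAP*

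**What the plan says.** SAP 6.5.8.9 turns PROWL answers into 0-100 scores, where 100 is best. Symptoms form four groups: double images, glare, halo and starbursts. One scoring row covers preoperative (PRQ) questions 45-64 and postoperative (POQ) questions 42-61. Its worked example for PRQ60, the starburst gate question, gives four options:

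- "Yes, when wearing AND when not wearing glasses or contact lenses = 0"
- "Yes, but ONLY when NOT wearing glasses or contact lenses = 100/3"
- "Yes, but ONLY when wearing glasses or contact lenses = 200/3"
- "No, not at all = 100"

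The other example, frequency item PRQ61a, has an option beginning "I do not wear glasses or contact", which is scored N/A. The gate example shows no such option. A group score is the mean of the items answered, and N/A items are left out. The planned output is: "Domains presented in Tables 3 and 4 will be summarized by study visit using continuous descriptive statistics including change from baseline".

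Protocol 8.5 describes the symptom output differently: "Subjective results will be presented as percentages", in categories of better and worse, alongside analyses of change from baseline.

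**The concern.** The gate item combines two facts: whether the symptom is present, and in which correction state it is noticed. The procedure is meant to alter the second. Protocol 3.3 names less need for glasses or contact lenses as the principal benefit, and Appendix B section 7.0 asks subjects to give up contact lenses for the study. Someone who no longer wears correction cannot truthfully choose either option that refers to wearing it. The set of available answers therefore differs before and after surgery, and part of the change from baseline may reflect spectacle wear alone. There is no control arm in which the artefact could be seen.

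Glare, halo, starbursts and double images are patient-reported safety outcomes. A count of subjects who got better or worse would help the reader judge them, and that is the output the SAP no longer contains.

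**Working it through.** **Inputs.** Gate scores of 0, 33.3, 66.7 and 100, the mean-of-answered-items rule and the N/A rule come from SAP 6.5.8.9. Each group has five numbered questions (for example "Starburst: 60-64"); the number of lettered sub-items is not given. Change is postoperative minus baseline (SAP 6.5.6.1).

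**The SAP's own figures.** Equal steps over k options give 100 × i/(k - 1). With k = 4 the scores are 0, 33.3, 66.7 and 100, as stated for PRQ60. With k = 5 they are 0, 25, 50, 75 and 100, as stated for PRQ61a. Both sets reproduce.

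**Item change.** Take a subject who wears no correction after surgery and has the symptom. The only truthful answer is 'only when not wearing', which scores 33.3.

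| Baseline answer | Baseline score | Change | What really happened |
|---|---|---|---|
| Both | 0 | 33.3 - 0 = +33.3 | symptom still present |
| Only without correction | 33.3 | 33.3 - 33.3 = 0 | symptom still present |
| Only with correction | 66.7 | 33.3 - 66.7 = -33.3 | symptom still present |
| None | 100 | 33.3 - 100 = -66.7 | new symptom |

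A new symptom noticed both with and without correction would cost 100. For a non-wearer the most it can cost is 66.7.

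**Cohort mean.** Let a and c be the shares of symptomatic baseline subjects who answer 'both' and 'only with'. If all of them stop wearing correction and all still have the symptom, the mean artefact on the item is 33.3 × (a - c). The documents give neither share, so these are assumed values:

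- a = 0.6, c = 0.1: 33.3 × 0.5 = +16.7
- a = c: 0
- a = 0.2, c = 0.5: 33.3 × (-0.3) = -10.0

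**Group score.** A 33.3-point item shift becomes 33.3/m when m items are answered: 33.3/3 = 11.1, 33.3/5 = 6.7, 33.3/9 = 3.7. Because N/A items leave the denominator, the gate weighs more in non-wearers. With five items and the other four fixed at 50, baseline 'both' goes from (0 + 200)/5 = 40.0 to (33.3 + 200)/5 = 46.7. Baseline 'only with' goes from (66.7 + 200)/5 = 53.3 to the same 46.7.

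**Percentages.** In SAP 6.5.8.9 the only PROWL percentages are per response option for POQ 71-78 (satisfaction with surgery), which have no baseline. SAP 6.6 lists three questionnaire changes: merging visual function into near vision, not summarizing expectations, and not summarizing the remaining questions. The loss of the better/worse percentages is not among them.

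**The case against.** A reader might infer that the scoring favours the device, because the worst score is out of reach after surgery. The documents do not support that as a net effect. The same four options make an unchanged symptom look worse for anyone who answered 'only with' before surgery. That answer is plausible in a population entering with uncorrected acuity of 20/40 or worse and sphere up to -10 D, since such subjects may spend little time uncorrected. If a non-wearer with the symptom were scored 0, the SAP score would be 33.3 points more favourable in every row. But that rule would itself turn an unchanged 'only without' symptom into a 33.3-point loss, so it is not a neutral yardstick.

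A reader might also infer that only means will be reported. SAP 6.5.6.1 adds SD, median, minimum and maximum, and every response is listed by subject and visit. Extreme changes will be visible, although none of this counts subjects who improved or worsened.

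Three further points stand. The POQ gate wording is not in the documents; a shared scoring row suggests that it matches but does not prove it. The gate is diluted by other items, and a constant symptom can still score 0 on a frequency item. The output is descriptive, lies outside the adverse-event incidence analysis, and plays no part in study success. SAP section 4 says that the SAP supersedes the protocol's statistical methods, so the missing percentages are also in part a documentation gap.

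**Conclusion.** The point holds in this form: change from baseline on the gate item mixes spectacle wear with symptom change. If the POQ gate has the same four options and the subject wears no correction after surgery, an unchanged symptom scores as +33.3, 0 or -33.3, and a new symptom as -66.7 instead of -100. That is about 6.7 group-score points per 33.3 item points if five items are answered. The net direction is unknown without the baseline answers. The missing better/worse percentages, and the silence of SAP 6.6 about them, are a separate gap that depends on none of these assumptions. Neither matter affects the primary endpoints. Both are worth correcting because the outcome concerns safety and the data are already collected.

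**What to change.** 1. Take the gate item out of the change-from-baseline score for each symptom group.
2. Report it as symptom present or absent, with a pre/post shift table (never, new, persisting, resolved) at Months 3, 6 and 9.
3. Restore the protocol 8.5 output as percentages of subjects better, the same or worse. Base these on the group score without the gate item, or on the graded frequency, severity and bother items; a yes/no item cannot show better or worse.
4. List the scoring change in SAP 6.6.

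The cost is a small departure from the planned normalization and one extra table. No new data are needed.

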	14	8	Mainly vision Mainly other reason Both vision and other reasons No scoring needed
Driving	15-17	9-11	No difficulty = 100 A little difficulty = 75 Moderate difficulty = 50 Extreme difficulty = 25 Never drive during the daytime because of vision, or Never drive at night because of vision or Never drive in these conditions because of vision = 0 Never drive during the daytime for other reasons, or Never drive at night for other reasons, or Never drive in these conditions for other reasons = N/A
	18	12	No difficulty at all =100 A little difficulty = 200/3 Moderate difficulty = 100/3 A lot of difficulty = 0
	Domain score questions ans		es of scores of all questions)/(total number of

	Note: Questions with answers as N/A will be treated as not answered and excluded from the calculation. Questions PRQ12, 13, 14 (or POQ6, 7, 8) are excluded from the domain score calculation.		
	34, 35, 36	28, 29, 30	Yes = 0 No = 100
Vision Clarity	34a, 35a, 36a	28a, 29a, 30a	Very = 0 Somewhat = 25 A little = 50 Not at all = 75
Vision Clarity	Domain score = (sum of scores of all questions within the domain)/(total number of questions answered) Note: When 34 is No, 34A should not be answered. However, in case 34 is No and 34A is answered, ignore 34 result from the domain score calculation and only use 34a result. Apply the same rule when the discrepancy happens to 35 (35A), or 36 (36A), or 28 (28A), or 29 (29A), or 30 (30A).		

 Table 5. PROWL Question Categories and Questions to be Analyzed

Topics - Table Summary with Descriptive Statistics	PROWL-PRQ Questions	PROWL-POQ Questions
Vision Satisfaction	37	34
Vision Clarity	5	5
Satisfaction with LASIK Surgery		71-78

Table 6a. Normalization Scores for PROWL Questions in Table 4

Topics - Table Summary with Descriptive Statistics	PROWL-PRQ Questions	PROWL-POQ Questions	Normalized Score
Vision Satisfaction	37	34	Completely satisfied = 100 Very satisfied = 80 Somewhat satisfied = 60 Somewhat dissatisfied = 40 Very dissatisfied = 20 Completely dissatisfied = 0
Vision Clarity	5	5	Perfectly clear = 100 Pretty clear = $200/3$ Somewhat clear = $100/3$ Not clear at all = 0
Satisfaction with LASIK Surgery		71-78	Scoring of each of these questions should be provided as percentages for each possible response.

Statistical Analysis Plan Version 1.0 / Protocol Number: 884

	Example 1) POQ72:
	Currently, how satisfied or
	dissatisfied are you with
	how long it took to see
	improvement in your vision
	after LASIK surgery?

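### The PROWL Vision Clarity score enters each pair answered Yes twice, so Yes with Not at all scores 37.5 while the contradictory No with Not at all scores 75

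*SAP*

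**What the plan says.** The Vision Clarity domain in SAP 6.5.8.9, Table 3, covers PRQ 34 to 36a before surgery and POQ 28 to 30a after it. That is three Yes/No gate items, each with one follow-up item. The normalized-score table gives the gate 0 for Yes and 100 for No, and gives the follow-up "Very = 0 Somewhat = 25 A little = 50 Not at all = 75".

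The text of the section sets the general rule: "Domain score for each subject will be provided as the average score of all questions within a domain after normalization". The Vision Clarity row repeats it: "Domain score = (sum of scores of all questions within the domain)/(total number of questions answered").

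Two notes deal with the pairing. The skip pattern is "When 34 is No, 34A should not be answered". If the gate is No and the follow-up is answered anyway, the instruction is to "ignore 34 result from the domain score calculation and only use 34a result"; the same applies to the other pairs. Nothing covers the ordinary case of a Yes with its follow-up answered.

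The domain scores are to be "summarized by study visit using continuous descriptive statistics including change from baseline". Protocol 5.2.3 leaves scoring to the SAP, so this table is what will be programmed.

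**The concern.** When the gate is No, the pair contributes one entry of 100. When the gate is Yes, it contributes two entries: a 0 for the gate and the follow-up value. A Yes is therefore penalised twice, and the weight of a pair in the domain depends on how it was answered.

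This makes the rule internally incoherent. Two records with the same follow-up answer get different scores, and the invalid one gets the higher score. The effect also carries into change from baseline, because the number of Yes answers, and with it the denominator, can differ between visits. Vision Clarity is one of six pre/post PROWL domains in SAP Table 3. SAP 6.5.8 lists the prespecified domain results among the safety summaries, and SAP 5 says the study results are intended for a PMA supplement.

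**Working it through.** **Inputs (all from SAP 6.5.8.9).** Gate: Yes = 0, No = 100. Follow-up: Very 0, Somewhat 25, A little 50, Not at all 75. Domain score = sum of answered items / number answered. The only rule that drops a gate item applies to No with an answered follow-up.

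**Scale check.** Five equal steps from 100 to 0 are 100, 75, 50, 25, 0. The follow-up values 75/50/25/0 fit that scale exactly, with the gate's No taking the 100. A stand-alone four-level item in equal steps would be 100, 66.7, 33.3, 0. The SAP uses that spacing for its other four-level items, for example PRQ 18, PRQ 19 and PRQ 5.

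**One pair.**

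| Answer | SAP rule | Pair scored once |
|---|---|---|
| No, follow-up blank | 100 | 100 |
| Yes, Not at all | (0 + 75)/2 = 37.5 | 75 |
| Yes, A little | (0 + 50)/2 = 25 | 50 |
| Yes, Somewhat | (0 + 25)/2 = 12.5 | 25 |
| Yes, Very | (0 + 0)/2 = 0 | 0 |
| No, Not at all (contradictory) | 75 | 75 |

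The contradictory record scores 75/37.5 = 2 times the consistent record with the same follow-up answer.

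**Domain score, Yes/Not at all pairs with the rest No.**

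| Yes pairs | SAP rule | Each pair scored once |
|---|---|---|
| 1 | (0 + 75 + 100 + 100)/4 = 68.75 | (75 + 100 + 100)/3 = 91.67 |
| 2 | (0 + 75 + 0 + 75 + 100)/5 = 50.00 | (75 + 75 + 100)/3 = 83.33 |
| 3 | (3×0 + 3×75)/6 = 37.50 | (3×75)/3 = 75.00 |

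**General form.** With three complete, consistent pairs, the two methods share a numerator, because the extra gate entry is 0. With m Yes pairs the denominators are 3 + m and 3, so the SAP score is 3/(3 + m) of the once-per-pair score: 0.75, 0.60 and 0.50 for m = 1, 2, 3. They agree at m = 0, and otherwise only when the numerator is 0, that is, all three pairs Yes/Very.

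**Ranking across subjects.** Three Yes/Not at all pairs score 37.5. One Yes/Very pair with two No scores (0 + 0 + 100 + 100)/4 = 50. Scored once per pair, the order reverses: 75 against (0 + 100 + 100)/3 = 66.67.

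**Change from baseline, other two pairs No.**
- Yes/Not at all to No: 100 − 68.75 = 31.25, against 100 − 91.67 = 8.33.
- Yes/Very to Yes/Not at all: 68.75 − 50 = 18.75, against 91.67 − 66.67 = 25.

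**The case against.** The strongest reply is that the averaging may be deliberate. In the Subject Symptoms row, a gate question such as PRQ 60 is scored 0 to 100 and averaged with its follow-ups. Where the SAP wants gate questions left out, it says so, as in Driving: "Questions PRQ12, 13, 14 (or POQ6, 7, 8) are excluded from the domain score calculation". For Vision Clarity the authors considered the pairing and dropped the gate only for conflicting answers.

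The Subject Symptoms comparison does not carry over, because that row sets the best state at 100 and the Vision Clarity follow-up cannot exceed 75. The Driving exclusion shows that the authors could have written such a rule, but not that the omission here was intended. Deliberate averaging also would not explain why conflicting answers score higher than consistent ones.

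Parts of the objection stand. A reader might infer that the SAP assigns 75 to the pair as a whole, so that 37.5 contradicts a stated figure. It does not: 75 is the value of the follow-up item, no worked example is given, and normalization is referred to a cited paper that is not available here. The item wording is not in the documents either, so a clinical reading such as a symptom that is present but not bothersome goes beyond them. Nor is every pair counted twice, since a pair answered No enters once. Nor is every subject with a Yes affected, since three Yes/Very pairs give 0 either way. Within a single pair, both methods rank the five consistent answers in the same order.

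**Conclusion.** Wrong as written, minor severity. It follows from the SAP text alone that a pair answered Yes enters the average twice and that a contradictory record can score twice a consistent one. With complete, consistent answers, domain scores are 25%, 40% or 50% below the once-per-pair value for one, two or three Yes answers, except that all three Yes/Very gives 0 under both methods.

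That each pair was meant as one 100/75/50/25/0 scale is an inference. It is well supported by the 75 ceiling and by the discrepancy rule, which lets the follow-up stand alone, but the SAP does not state it.

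A reader might also infer that the study's conclusions are at risk. The documents do not support that. The domain is summarized descriptively, there are no secondary effectiveness endpoints, and statistical success rests on the three primary endpoints, which do not use PROWL data. The item responses are also listed by subject and visit, so the domain can be rescored without loss.

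**What to change.** Replace the Vision Clarity scoring note with a rule that scores each gate and follow-up pair once:

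- Follow-up answered: use its value (75/50/25/0), whatever the gate says. This keeps the present treatment of discrepant records.
- Gate No and follow-up blank: 100.
- Gate Yes and follow-up blank, or both blank: not answered. As the SAP stands, a Yes with a blank follow-up enters as 0.
- Domain score: the mean over the pairs scored.

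Confirm the rule against the cited scoring reference before database lock. If that reference does average both items, the SAP should say so and reconcile it with the discrepancy rule and the 75 ceiling. The cost is one scoring note in the SAP and the matching line of code; no new data are needed.
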